7.3 Management of Adverse Events

AEs associated with pembrolizumab exposure may represent an immunologic etiology. These immune-related AEs (irAEs) may occur shortly after the first dose or several months after the last dose of pembrolizumab treatment and may affect more than one body system simultaneously. Therefore, early recognition and initiation of treatment is critical to reduce complications. Based on existing clinical trial data, most irAEs were reversible and could be managed with interruptions of pembrolizumab, administration of corticosteroids and/or other supportive care. For suspected irAEs, ensure adequate evaluation to confirm etiology or exclude other causes. Additional procedures or tests such as bronchoscopy, endoscopy, skin biopsy may be included as part of the evaluation. Based on the severity of irAEs, withhold or permanently discontinue pembrolizumab and administer corticosteroids. Dose modification and toxicity management guidelines for irAEs associated with pembrolizumab are provided in **Table 4**.

Table 4: Dose modification and toxicity management guidelines for immune-related AEs associated with pembrolizumab

General instructions:				

 1. Corticosteroid taper should be initiated upon AE improving to Grade 1 or less and continue to taper over at least 4 weeks. 2. For situations where pembrolizumab has been withheld, pembrolizumab can be resumed after AE has been reduced to Grade 1 or 0 and corticosteroid has been tapered. Pembrolizumab should be permanently discontinued if AE does not resolve within 12 weeks of last dose or corticosteroids cannot be reduced to ≤ 10 mg prednisone or equivalent per day within 12 weeks. 3. For severe and life-threatening irAEs, IV corticosteroid should be initiated first followed by oral steroid. Other immunosuppressive treatment should be initiated if irAEs cannot be controlled by corticosteroids. 				
Immune-related AEs	Toxicity grade or conditions (CTCAEv4.0)	Action taken to pembrolizumab	irAE management with corticosteroid and/or other therapies	Monitor and follow-up
Pneumonitis	Grade 2	Withhold	
 • Administer corticosteroids (initial dose of 1-2mg/kg prednisone or equivalent) followed by taper 	
 • Monitor subjects for signs and symptoms of pneumonitis • Evaluate subjects with suspected pneumonitis with radiographic imaging and initiate corticosteroid treatment • Add prophylactic antibiotics for opportunistic infections
	Grade 3 or 4, or recurrent grade 2	Permanently discontinue		

Diarrhea / colitis	Grade 2 or 3	Withhold	
 Administer corticosteroids (initial dose of 1-2mg/kg prednisone or equivalent) followed by taper 	
 Monitor subjects for signs and symptoms of enterocolitis (i.e. diarrhea, abdominal pain, blood or mucus in stool with or without fever) and of bowel perforation (i.e. peritoneal signs and ileus). Subjects with \geq Grade 2 diarrhea suspecting colitis should consider GI consultation and performing endoscopy to rule out colitis. Subjects with diarrhea/colitis should be advised to drink liberal quantities of clear fluids. If sufficient oral fluid intake is not feasible, fluid and electrolytes should be substituted via IV infusion.
	Grade 4	Permanently discontinue		
AST / ALT elevation or Increased Bilirubin	Please see section 6.2.3 regarding the management of overlapping hepatotoxicity with rucaparib and pembrolizumab.			
Type 1 diabetes mellitus (T1DM) or Hyperglycemia	Newly onset T1DM or Grade 3 or 4 hyperglycemia associated with evidence of β -cell failure	Withhold	
 Initiate insulin replacement therapy for subjects with T1DM Administer anti-hyperglycemic in subjects with hyperglycemia 	
 Monitor subjects for hyperglycemia or other signs and symptoms of diabetes.
Hypophysitis	Grade 2	Withhold	
 Administer corticosteroids and initiate hormonal replacements as clinically indicated. 	
 Monitor for signs and symptoms of hypophysitis (including hypopituitarism and adrenal insufficiency)
	Grade 3 or 4	Withhold or permanently discontinue ¹		
Hyperthyroidism	Grade 2	Continue	
 Treat with non-selective beta-blockers (e.g. propranolol) or thionamides as appropriate 	
 Monitor for signs and symptoms of thyroid disorders.
	Grade 3 or 4	Withhold or Permanently discontinue ¹		
Hypothyroidism	Grade 2-4	Continue	
 Initiate thyroid replacement hormones (e.g. levothyroxine or 	
 Monitor for signs and symptoms of thyroid disorders.

			liothyronine) per standard of care	
Nephritis and renal dysfunction	Grade 2	Withhold	
 Administer corticosteroids (prednisone 1-2mg/kg or equivalent) followed by taper. 	
 Monitor changes of renal function
	Grade 3 or 4	Permanently discontinue		
Myocarditis	Grade 1 or 2	Withhold	
 Based on severity of AE, administer corticosteroids 	
 Ensure adequate evaluation to confirm etiology and/or exclude other causes
	Grade 3 or 4	Permanently discontinue		
All Other immune-related AEs	Grade 3, or intolerable/persistent Grade 2	Withhold	
 Based on severity of AE administer corticosteroids 	
 Ensure adequate evaluation to confirm etiology or exclude other causes
	Grade 4 or recurrent Grade 3	Permanently discontinue		
NOTES:				

 Withhold or permanently discontinue pembrolizumab is at the discretion of the investigator or treating physician. For subjects with Grade 3 or 4 immune-related endocrinopathy where withholding of pembrolizumab is required, pembrolizumab may be resumed when AE resolves to \leq Grade 2 and is controlled with hormonal replacement therapy or achieved metabolic control (in case of T1DM) 				

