6.0 TREATMENT PLAN

6.1 Drug Administration

6.1.1 Treatment

Both dexamethasone and pembrolizumab are standard medications and will be used from commercial standard supply. The first dose of trial treatment is considered to be first dose of dexamethasone. Trial treatment should begin within 14 days of enrollment.

Table 2: Treatment drugs

Drug	Dose/Potency	Dose Frequency	Route of Administration	Regimen/Treatment Period
Pembrolizumab	200 mg	Q3W	IV infusion	Day 1 of each 21-day cycle

Dexamethasone will be administered orally, prior to each dose of pembrolizumab for 3 cycles in the following cohorts:

Cohort 1: 4 mg BID for 7 days, followed by taper 2 mg BID for 1 day and 1 mg BID and 3 day wash out.

Cohort 2: 4mg BID for 10 days, followed by 2 mg BID for 2 days, 1 mg BID for 1 day and 3 day wash out.

Cohort 3: 4 mg BID for 13 days, 2mg BID for 3 days, 1 mg BID for 1day and 3 day wash out

Pembrolizumab 200 mg (IV) will be administered per institutional standard of care guidelines.

Subjects will be given a pill diary and instructed to complete for each day of administration of Dexamethasone. Missed and/or vomited doses should be recorded on the diary as such. Subjects will be asked to bring their pill diary to each study visit.

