6.3 Dexamethasone dose modification: CBC and Metabolic profile will be monitored once weekly while on DEX. Any Grade III or greater non-hematological side effect will result in holding the DEX with resumption only when AE is Grade 1 or lower, and patient is asymptomatic. If symptomatic, DEX will be permanently discontinued.

6.4 Diet/Activity/Other Considerations: No special considerations. In diabetics, we will encourage stricter adherence to sugar free meals

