6.5 Subject Withdrawal/Discontinuation Criteria

Subjects may withdraw consent at any time for any reason or be dropped from the trial at the discretion of the investigator should any untoward effect occur. In addition, a subject may be withdrawn if enrollment into the trial is inappropriate, the trial plan is violated, or for administrative and/or other safety reasons. Specific details regarding discontinuation or withdrawal are provided in Section 7.5.

A subject must be discontinued from study treatment for any of the following reasons:

- The subject or legal representative (such as a parent or legal guardian) withdraws consent.
- Confirmed radiographic disease progression

Note: A subject may be granted an exception to continue treatment with confirmed radiographic progression if clinically stable or clinically improved at the discretion of the investigators.

- Unacceptable adverse experiences as described in Section 6.2 and 7.3
- Intercurrent illness that prevents further administration of treatment
- Investigator's decision to withdraw the subject
- The subject has a confirmed positive serum pregnancy test
- Noncompliance with trial treatment or procedure requirements
- The subject is lost to follow-up
- Completed 24 months of uninterrupted treatment with pembrolizumab
- Administrative reasons

The End of Treatment and Follow-up visit procedures are listed in Section 7.5.1. After the end of treatment, each subject will be followed for 30 days for adverse event monitoring. Serious adverse events will be collected for 30 days after the end of treatment as described in Section 9.0). End of treatment and survival follow-up procedures are listed in section 7.2. Subjects who discontinue for reasons other than progressive disease will have post-treatment follow-up

for disease status until disease progression, initiating a non-study cancer treatment, withdrawing consent or becoming lost to follow-up. After documented disease progression each subject will be followed every 6 months through the medical record for overall survival until death, withdrawal of consent, or the end of the study, whichever occurs first.

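### Table 4's row for raised AST/ALT or bilirubin only points to a non-existent section on a drug not used in this trial, so no stated row sets the pembrolizumab action for liver events

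*Combined protocol and SAP*

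**What the plan says.** Table 4 in Section 7.3 sets pembrolizumab dose modification for immune-related events. It has nine named rows: pneumonitis, diarrhea/colitis, AST/ALT or bilirubin, type 1 diabetes/hyperglycemia, hypophysitis, hyperthyroidism, hypothyroidism, nephritis and myocarditis. A catch-all row for all other immune-related events follows. The whole content of the liver row is: "Please see section 6.2.3 regarding the management of overlapping hepatotoxicity with rucaparib and pembrolizumab".

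The catch-all row withholds pembrolizumab for "Grade 3, or intolerable/persistent Grade 2" and discontinues it permanently for "Grade 4 or recurrent Grade 3".

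Three other provisions bear on liver events:

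- **General rules, Section 7.3.** The text above the table says: "Based on the severity of irAEs, withhold or permanently discontinue pembrolizumab and administer corticosteroids". The general instructions add that, after withholding, "pembrolizumab can be resumed after AE has been reduced to Grade 1 or 0 and corticosteroid has been tapered". They require a permanent stop if the event has not resolved, or steroids cannot be brought down to 10 mg prednisone or equivalent per day, within 12 weeks.
- **Dexamethasone, Section 6.3.** "CBC and Metabolic profile will be monitored once weekly while on DEX". Dexamethasone is held for any non-hematological side effect of Grade III or above.
- **Withdrawal, Section 6.5.** A subject may be "dropped from the trial at the discretion of the investigator should any untoward effect occur". Stopping is mandatory for unacceptable adverse experiences as set out in Sections 6.2 and 7.3.

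On the study drugs, Section 6.1.1 says: "Both dexamethasone and pembrolizumab are standard medications and will be used from commercial standard supply".

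**The concern.** Liver toxicity has its own row in the safety table, but that row leads nowhere. Because liver events are named, a literal reader would not count them among the other events covered by the catch-all row. The investigator therefore has to infer the grade at which pembrolizumab is withheld and the grade at which it is stopped for good. Section 6.5 adds weight, because it ties mandatory discontinuation to Sections 6.2 and 7.3. For liver events, the first has no text and the second has only the dead pointer. What is at stake is consistent handling of patients with raised liver tests.

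**Working it through.** The plan gives no figure to reproduce, so the check sets the passages side by side.

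**1. Does Section 6.2.3 exist?** No. The table of contents goes from 6.2 directly to 6.3, although it lists third-level headings elsewhere (6.4.1, 6.4.2, 6.5.1). The body agrees. Section 6.2 covers infusion reactions and interruptions unrelated to adverse events, has no hepatic text, and sends immune-related events to Section 7.3. A reader who takes the pointer to mean Section 6.2 as a whole is sent back to Section 7.3. Contents and body agree, and the row is a complete sentence, so this is not an effect of redaction or text extraction.

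**2. Is rucaparib part of the trial?** No. The treatment section names dexamethasone and pembrolizumab only. Rucaparib appears nowhere else in the document.

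**3. How does the row compare with the others?** Named rows: 9. Rows with both a grade or condition and a pembrolizumab action: 8. Rows with neither: 9 − 8 = 1, the liver row.

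**4. What rules remain for pembrolizumab under each reading?**

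| Rule for pembrolizumab in a liver event | Catch-all row applies | Catch-all row does not apply |
|---|---|---|
| Grade-based conditions for withholding | 2 (Grade 3; intolerable or persistent Grade 2) | 0 |
| Grade-based conditions for permanent stop | 2 (Grade 4; recurrent Grade 3) | 0 |
| 12-week permanent-stop rules after withholding | 2 (event unresolved; steroids not reduced) | 2 |
| Severity-based instruction and investigator discretion | yes | yes |

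The gap is thus the grade for withholding and the grade for an immediate permanent stop. The 12-week rules operate once pembrolizumab has been withheld; they do not say when to withhold it.

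**5. Does the choice of row change the action?** Yes, if an investigator reasons by analogy. Under the catch-all row, a first Grade 3 event means withhold. Under the nephritis row, which also concerns organ function, Grade 3 means permanent discontinuation and any Grade 2 means withhold.

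**6. Does the dexamethasone rule fill the gap?** Only for dexamethasone. A Grade III or greater liver event leads to a hold, with resumption at Grade 1 or lower if the patient is asymptomatic and a permanent stop if symptomatic. It does not govern pembrolizumab. In the calendars, pembrolizumab continues in the C4+ column, where dexamethasone is no longer marked.

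**7. Can the question arise?** Yes. The calendar item Comp is marked in all 3 pembrolizumab columns (C1D1, C2 and 3 D1, C4+). Comp is assumed to be the comprehensive metabolic panel in the abbreviation list. The number of patients who would be affected cannot be derived from the documents.

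**The case against.** The strongest reply is that the protocol still gives a workable path. The catch-all row is the obvious fallback, the severity-based instruction and the 12-week limits apply to any immune-related event, and dexamethasone has a definite grade-based hold. Sections 6.1.1 and 12.1 also say pembrolizumab is given according to institutional standards. There is one study center, and a safety committee meets monthly. Discretion is normal in this table: the action for Grade 3 or 4 hypophysitis and hyperthyroidism is left to the physician by a table note.

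Much of this stands, and it limits the consequence. It does not close the gap. The severity instruction gives no grades and refers to Table 4 for them. The institutional-standard wording concerns administration and names no liver threshold. Where the table leaves a choice to the physician, it says so; the liver row does not.

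Two stronger readings are tempting, and the documents do not support them:

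- **That there is no guidance at all for liver events.** The provisions just listed refute this.
- **That the resumption rule fails patients with liver metastases**, because Table 1 in Section 5.1 admits AST/ALT up to 5 x ULN while resumption requires Grade 1 or 0. The documents give no CTCAE cut-points for AST/ALT, so the grade at 5 x ULN cannot be established from them. The eligibility limit is also unsettled: the trial summary states 2.5 x ULN with no exception for liver metastases.

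**Conclusion.** The point holds as a patient-safety wording error. One of nine named rows in Table 4 cannot be followed, and no text says which row sets the grades for withholding or permanently stopping pembrolizumab in liver events. Depending on the reading, the number of grade-based conditions is two for each action or none for either. The conclusion rests on the text alone, apart from the assumption about Comp, which bears only on how often the question could arise. A reader might infer some effect on the trial's inference; there is none on the FLT-PET endpoint, alpha, power or sample size. The correction should be made, but the surrounding rules keep its consequence modest.

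**What to change.** Delete the reference to Section 6.2.3 and rucaparib. Then do one of the following in the liver row:

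- State that the actions of the catch-all row apply: withhold for Grade 3 or for intolerable or persistent Grade 2, and permanently discontinue for Grade 4 or recurrent Grade 3. One sentence is enough.
- Enter liver-specific grade-based actions for AST/ALT and bilirubin, with the thresholds set by the investigator.

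As a purely clerical matter, correct the two table numbers in Section 6.2 in the same amendment. Infusion reactions are in Table 3, cited there as Table 4. Immune-related events are in Table 4, cited there as Table 7, although the list of tables ends at 4.

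The cost is protocol wording only, with no change to endpoints, sample size or visit schedule.

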7.4 Prohibited Concomitant Medications

Subjects are prohibited from receiving the following therapies during the Screening and Treatment Phase of this trial:

- Antineoplastic systemic chemotherapy or biological therapy
- Immunotherapy not specified in this protocol
- Chemotherapy not specified in this protocol
- Investigational agents
- Radiation therapy
 - **Note:** Radiation therapy to a symptomatic solitary lesion or to the brain may be allowed at the investigator's discretion.
- Live vaccines within 30 days prior to enrollment and while participating in the trial. Examples of live vaccines include, but are not limited to, the following: measles, mumps, rubella, varicella/zoster, yellow fever, rabies, BCG, and typhoid vaccine.

7. Daily systemic glucocorticoids with dose >10mg of prednisone (or its equivalent) for any purpose other than to modulate symptoms from an event of clinical interest of suspected immunologic etiology.

Subjects who, in the assessment by the investigator, require the use of any of the aforementioned treatments for clinical management should be removed from the trial. Subjects may receive other medications that the investigator deems to be medically necessary.

7.5 Withdrawal/Discontinuation

When a subject discontinues/withdraws prior to trial completion, all applicable activities scheduled for the final trial visit should be performed at the time of discontinuation. Any adverse events which are present at the time of discontinuation/withdrawal should be followed in accordance with the safety requirements outlined in Section 9.0.

7.5.1 End of Treatment Follow-up Visits

The mandatory Safety Follow-Up Visit should be conducted within 30 +/- 10 days after the last dose of pembrolizumab. Subjects with an AE of Grade >1 will be further followed until the resolution of the AE to Grade 0-1 or until beginning of a new antineoplastic therapy, whichever occurs first. Procedures should be conducted according to the Treatment Calendar in Section 7.2. SAEs that occur within 30 days of the end of treatment should be followed and recorded.

7.5.2 Survival Follow-up

Once a subject experiences confirmed disease progression or starts a new anti-cancer therapy, the subject will be followed through his/her medical record and assessed for survival status until death or 2 years. Data will be collected every 6 months.

8.0 IMAGING AND MEASUREMENT OF DISEASE

Response and progression will be evaluated in this study using the international criteria proposed by the Response Evaluation Criteria in Solid Tumors (RECIST) Committee, version 1.1 (32)

Immunotherapy drugs can initially cause inflammation in the early stages of treatment. Immune-related RECIST (irRECIST) utilizes RECISTv1.1 but considers an inflammatory response (or “pseudo-progression”) as normal. The main difference between RECISTv1.1 and irRECIST is that patients can stay on trial after the first progressive disease (PD) assessment (as per RECISTv1.1) if using immune-related RECIST criteria. This PD per RECISTv1.1 is then re-labeled as immune related stable disease (irSD) per irRECIST (33) and requires addition of unidimensional measurements of all new lesions (that meet the definition of target lesion) to be added to the sum of longest diameters (SLD) calculation for response assessment. Importantly, immune-related progression (irPD) must be confirmed by a follow-up scan at

least 4 weeks (within 4-8 weeks) following the initial PD/irSD assessment in order to take the patient off the trial.

Subjects that are deemed to have clinical progression and unstable should not be continued on therapy after PD (per RECISTv1.1) and are therefore not required to have repeat tumor imaging for confirmation as per irPD definition. It is at the discretion of the site investigator whether to continue a subject on study treatment until repeat imaging is obtained. This clinical judgment decision by the site investigator should be based on the subject's overall clinical condition, including performance status, clinical symptoms, and laboratory data.

Definitions

Evaluable for objective response: Only those patients who have measurable disease present at baseline, have received at least 2 cycle(s) of therapy, and have had their disease re-evaluated will be considered evaluable for response. These patients will have their response classified according to the definitions stated below. (Note: Patients who exhibit objective disease progression prior to the end of cycle 1 will also be considered evaluable.)

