respectively. The secondary endpoints are the changes in SASP and LPFM expression levels between cycle 0 and cycle 1 as well as the expression level of GR at cycle 0. The association between the FLT-PET response and the changes in the expression levels of each of SASP and LPFM will be examined using logistic regression models. The expression levels of SASP and LPFM between cycle 0 and cycle 1 will be examined using a paired t-test, if needed, after data transformation (such as log or square root transformation). The association between the FLT-PET response and the GR expression level will be assessed using logistic regression models. The trajectories from cycle 0 to cycle 4 for the expression levels of each of SASP and LPFM will be examined to see if the expression levels increase monotonically across cycles. To do this, linear mixed-effects models will be used, if needed, after data transformation. In addition, in case that either Cohort B or C becomes the optimal duration, we will descriptively compare the changes in SASP and LPFM expression levels from cycle 0 to cycle 1 between lead-in cohorts. Because these are a discovery study to generate hypotheses, no multiple comparison correction will be made. However, if either the sample size is less than 12 patients or a level (i.e., response vs. non-response) has less than 5 events; all secondary objectives will be exploratory and will be summarized descriptively. All statistical analyses will be based on complete data and no missing data analysis will be performed.

The secondary objective is to assess the effect of DEX on pembrolizumab in terms of overall response rate (ORR), which is the primary endpoint. Based on our previous pre-clinical and clinical studies, we hypothesize that the true ORR of DEX followed by pembrolizumab will be at least 33% (i.e., $p_1 = 0.33$) vs. the historical control whose ORR is at most 7% (i.e., $p_0 = 0.07$). The ORR will be statistically evaluated when the FLT-PET response trial enters the third stage, where the number of patients with the selected optimal DEX duration will be 21. Otherwise, the ORR will be summarized descriptively. The null hypothesis ($p_0 = 7\%$) will be rejected if five or more responses are observed in 21 patients, which yields a 1-sided type I error rate of 5% and power of 87% when the true ORR is 33% (i.e., $p_1 = 33\%$).

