We will also to explore the associations between ORR and the changes in expression levels of each of SASP and LPFM from cycle 0 to cycle 1, (ii) to explore the association between ORR and GR expression at cycle 0, and (iii) to explore the progression-free survival (PFS). The associations between ORR and the changes of SASP and LPFM and between ORR and the GR expression will be examined using logistic regression models and no multiple comparison correction will be made because these are a discovery study to generate hypotheses. The distribution of PFS will be summarized graphically using the Kaplan-Meier (KM) curve and the median PFS and associated 95% confidence interval will be estimated using KM estimate. If either the sample size is less than 12 patients or a level (i.e., response vs. non-response) has less than 5 events, the secondary objectives will be exploratory and will be summarized descriptively. All statistical analyses will be based on complete data and no missing data analysis will be performed.

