11.3 Population for Analysis

Intent-to-Treat Population: All patients consented and enrolled in the trial.

Evaluable Population: Only those patients who have received at least one cycle of therapy with dexamethasone and pembrolizumab will be considered evaluable.

Safety Evaluable Population: Patients who receive any treatment on protocol will be considered evaluable for safety.

11.4 Analysis of Primary Objective: The primary objective is to identify the smallest duration of fixed dose Dex that results in a >30% reduction in FLTPET. We will utilize a 2 stage design with 3 cohorts (see Statistical schema). The hypothesis is that the true “response” in FLTPET (reduction in FLTPET by >30% following Dex in at least 1 target lesion) will be 60% ($p_1=60$) vs. p_0 30% (based on preliminary data that chemotherapy such as docetaxel results in irreversible cell cycle arrest as measured by S-phase surrogate on FLT-PET (39)).

Secondarily, we will compare FLTPET “response” to GR expression and generation of SASP and immune effector cells. We will also track the trend in immune effector cell response at later time points (cycle 2 and 3) to test contributory effects of pembrolizumab and Dex on the immune phenotype in the blood.

11.5 Analysis of Secondary Objectives The secondary objective is to establish that the true ORR of Dex followed by pembrolizumab will be at least 33% ($p_1 = 0.33$) vs. docetaxel treatment (as the historical control) whose ORR is

$\leq 7\%$ ($p_0 = 0.07$). The ORR will be assessed at a 12 week FDG PET scan. The required sample size for both lead-in FLTPET response and phase 2 studies will range 21 to 31 patients. As secondary objectives, we will explore associations of the change in FLT-PET with ORR assessed by FDG-PET, level of plasma SASP, and immune cell activation. The change in FLT-PET will be compared by ORR using an unpaired t-test and the associations with the level of plasma SASP and immune cell activation will be examined by a correlation analysis. The power is not formally justified because these are exploratory

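### The plan does not name the ORR denominator, its response-evaluable rule would drop mostly treatment failures, and its PFS definition leaves out death

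*Combined protocol and SAP*

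**What the plan says.** **ORR.** Section 11.1 tests ORR once the trial reaches its third stage, when "the number of patients with the selected optimal DEX duration will be 21". The null of 7% "will be rejected if five or more responses are observed in 21 patients", with a stated one-sided type I error of 5% and 87% power at 33%. It does not say which analysis set those 21 patients form.

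Section 11.3 defines two efficacy sets and assigns neither to ORR: "Intent-to-Treat Population: All patients consented and enrolled in the trial", and an Evaluable set, "Only those patients who have received at least one cycle of therapy with dexamethasone and pembrolizumab will be considered evaluable". Section 11.5, on the secondary objectives, names no set.

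Section 8.0 (Definitions) adds another. Only patients with measurable baseline disease who "have received at least 2 cycle(s) of therapy, and have had their disease re-evaluated will be considered evaluable for response", with one exception: "Patients who exhibit objective disease progression prior to the end of cycle 1 will also be considered evaluable".

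Section 11.1 also states: "All statistical analyses will be based on complete data and no missing data analysis will be performed". Section 8.3 gives unscanned clinical decline its own label (symptomatic deterioration) but does not say that it counts as non-response.

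**PFS.** Section 8.3 measures PFS from treatment start to progression, without mention of death or censoring. Section 11.1 plans a Kaplan-Meier curve, and "the median PFS and associated 95% confidence interval will be estimated using KM estimate".

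**The concern.** The Section 8.0 set selects on outcome. A patient who dies, deteriorates or stops before two cycles, or who is never re-scanned, is unlikely to have been a responder. Such a patient leaves the denominator unless objective progression was shown before the end of cycle 1. Section 4.2.1 says that survival in this setting is often under six months, so early losses are plausible. Because no section chooses among the four sets, two analysts could report different ORRs from the same data, and the more restrictive choice gives the higher figure.

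For PFS, if a patient who dies without progression is censored, the reported median is a time-to-progression median under another name.

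What is at stake is the estimates. Section 11.2 says the results will help to design a more definitive study, so an inflated ORR or PFS would carry into its assumptions.

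**Working it through.** **Inputs from the plan:** n = 21, cut-off 5, p0 = 0.07, p1 = 0.33 (Section 11.1); drop-out up to 20% (Section 11.2). **Assumed, because the documents do not give them:** the share d of patients who are non-responders and excluded by Section 8.0, and the share f of first PFS events that are deaths without progression.

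**1. Reproduce the plan's figure (exact binomial).**
- P(X ≥ 5 | 21, 0.33) = 0.872, which matches the stated 87%.
- P(X ≥ 5 | 21, 0.07) = 0.0133, and P(X ≥ 4 | 21, 0.07) = 0.0551. Five is therefore the smallest cut-off that stays under 5%.

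**2. Effect on the estimate, x/n with x = 5.** All 21: 5/21 = 23.8% (Clopper-Pearson 95% CI 8.2-47.2). Dropping 1, 2, 3, 4 or 5 non-responders gives 25.0%, 26.3%, 27.8%, 29.4% or 31.2%. With four dropped, 5/17 has a 95% CI of 10.3-56.0. In general the rate is multiplied by 1/(1 − d). For d of 10-20%, a true 7% reads 0.07/0.9 = 7.8% to 0.07/0.8 = 8.75%.

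**3. Effect on the decision.**
- *No replacement.* Removing non-responders adds no responses, so whether five is reached does not change.
- *Replacement until 21 are evaluable* (not stated in the plan). The type I error on the all-treated scale is P(X ≥ 5 | 21, 0.07/(1 − d)): 0.0202 at d = 10%, 0.0318 at 20% and 0.0522 at 30%. It crosses 5% at d of about 29%.

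**4. Does a cut-off of five survive a larger treated set?** 21/0.8 = 26.25, rounded up to 27. P(X ≥ 5 | N, 0.07) is 0.037 at N = 27, 0.049 at N = 29 and 0.055 at N = 30. The cut-off is valid for N = 21-29.

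**5. Power if 33% refers to evaluable patients and 20% are non-evaluable.** The all-started ORR is 0.33 × 0.8 = 26.4%. Power of five or more responses is 0.686 with 21 started and 0.877 with 27.

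**6. Scan timing.** The first scheduled on-treatment response scan is C4D1 (Section 7.2): day 3 × 21 + 1 = 64, or day 3 × 28 + 1 = 85 with the 28-day cycle that Section 1.0 gives for Cohort 3, each ±7 days. A patient who stops early is re-evaluated only if the end-of-treatment scan, or an unscheduled one, is done.

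**7. PFS.** Take constant hazards, λp for progression and λd for death without progression, with f = λd/(λp + λd). The median with death as an event is ln 2/(λp + λd). With such deaths censored it is ln 2/λp. The ratio is 1/(1 − f): 1.11, 1.25 and 1.43 for f = 10%, 20% and 30%. An assumed true median of 3.0 months would read 3.3 to 4.3 months.

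**The case against.** The best defence is that the operative ORR rule is already fixed: five responses among the 21 patients at the selected duration. Read that way, an unscanned patient is simply not a response, and Section 8.0 is only a definition that Section 11 never invokes. This stands for the test, but not for the reported rate, whose denominator no section states.

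The plan also limits the loss of failures. Section 7.2 schedules an end-of-treatment FDG PET/CT. Section 7.5 asks for final-visit activities at discontinuation. Section 8.3 asks that progression be documented, if at all possible, even after treatment stops. Eligibility requires measurable disease and a life expectancy of at least six months. These provisions reduce the excluded group. They do not empty it, because patients who die or become too ill to be scanned remain outside.

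The sizes rest on assumptions. The 20% in Section 11.2 is a drop-out ceiling, not an estimate of Section 8.0 exclusions, and nothing in the documents supports a value for f. The ORR shift in the worked example, 5.6 points, lies well inside the confidence interval.

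On PFS, the upward direction depends on censoring, which is not stated. The definition does not require objective documentation, unlike duration of response in the same section, so a death from clinical progression could be dated as progression. The clear gap is death without progression.

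A reader might go further and infer that the ORR test is invalid, since four responses would be significant in 17 patients (p = 0.027) but not in 21 (p = 0.055). The documents do not support this: Section 11.1 fixes five in 21 and provides for no re-derived cut-off. Nor do they show that ORR and PFS will be overstated, only that permitted readings would overstate them.

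**Conclusion.** The concern holds in this form. The ORR denominator is undefined among four candidates. The Section 8.0 set, combined with complete-data analysis, would raise the ORR estimate by a factor of 1/(1 − d), for example from 23.8% to 29.4% if four of 21 are dropped as non-responders. The decision rule is unchanged without replacement and, with replacement, keeps its type I error below 5% until about 29% are excluded.

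PFS as defined omits death. If deaths without progression are censored, the median reads 11-43% too long, given assumed shares of 10-30% and constant hazards.

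Priority is modest: ORR is a secondary objective, PFS is exploratory, and the primary FLT-PET test is not affected by the Section 8.0 rule. The change is still worth making, because following two of the plan's own rules as written would favour the treatment.

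**What to change.** - **Sections 11.3 and 11.5.** Name one treated set at the selected duration as the ORR population. All patients who start dexamethasone fits Section 6.1.1, which treats that dose as the start of trial treatment. Another treated set would also settle the ambiguity, but this one includes patients who never reach pembrolizumab and so leaves out no early failures among treated patients.
- **Non-response.** Count patients without a post-baseline scan, including those labelled symptomatic deterioration, as non-responders.
- **Test.** Keep the cut-off of five (valid for N = 21-29) and the planned drop-out allowance.
- **Sensitivity analysis.** Report ORR in the Section 8.0 set, and state whether two cycles means started or completed.
- **Section 8.3.** Define PFS from start of treatment to the earlier of progression or death from any cause, censoring living progression-free patients at their last tumour assessment.
- **Follow-up text.** Align Sections 2.1, 6.5 and 7.5.2. The first follows patients until death. The second does not list death for patients who stop without progression. The third starts survival follow-up only after progression or new therapy.

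The cost is mainly wording. Deaths within 30 days of the last pembrolizumab dose are already collected as serious adverse events (Section 9.0), so the extra data are later death dates from the medical record. ORR and PFS may read slightly less favourably. If the 33% target was meant for evaluable patients and 20% prove non-evaluable, power is 69% with 21 started and 88% with 27, which is why the drop-out allowance should stay.
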